5.1 Efficacy assessments

5.1.1 CT and MRI scans; Tumour assessments (RECIST 1.1)

Following the baseline assessment, subsequent tumour assessments according to RECIST 1.1 should be performed every 8 weeks (± 1 week) for the first 72 weeks and then every 12 weeks (± 1 week) thereafter, relative to the date of randomisation and irrespective of treatment decisions, up to objective disease progression by RECIST 1.1.

The imaging modalities used for RECIST 1.1 assessment will be CT scans of the chest, abdomen and pelvis (or MRI where CT is contraindicated) with other regions as clinically indicated for the assessment of disease. Brain CT scan/MRI at baseline should be done for patients with known history of brain metastatic disease. Any other sites at which new disease is suspected should also be appropriately imaged. The methods of assessment of tumour burden used at baseline must be used at each subsequent follow-up assessment.

Radiological examinations performed in the conduct of this study should be retained at site as source data.

Coded copies of all scans, regardless of modality, are to be sent to an AstraZeneca appointed CRO for BICR.

All treatment decisions will be based on site assessment of scans. After the primary PFS analysis for each of the strata, central review of scans will no longer be required for that stratum and Investigators will be advised when to stop sending copies of the scans to the CRO conducting the central review. Patients who are determined to have progressed according to RECIST 1.1 criteria by the Investigator will have scans centrally reviewed for confirmation of objective disease progression. If disease progression is not confirmed at central review an additional RECIST 1.1 assessment may be requested preferably at the next scheduled RECIST 1.1 visit, if the central assessment is available in an appropriate timeframe.

It is important to follow the assessment schedule as closely as possible. If scans are performed outside of scheduled visit ± 1 week window interval and the patient has not progressed, every attempt should be made to perform the subsequent scans at their scheduled time points. Patients will be evaluated until objective radiological disease progression by RECIST 1.1 as per the study schedule (see [Table 3](#), and [Table 4](#) and [Table 5](#)), and then followed for survival, regardless of whether study treatment is discontinued or delayed and/or protocol violations, unless they withdraw consent.

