5.1.2 Tumour evaluation

RECIST 1.1 criteria will be used to assess patient response to treatment by determining PFS times and ORRs as appropriate to study endpoints. The RECIST 1.1 guidelines for measurable, non measurable, target and non target lesions and the objective tumour response criteria (CR, PR, SD or progressive disease [PD]) are presented in [Appendix F](#).

The methods of assessment of tumour burden used at baseline - CT or MRI scans of chest, abdomen, and pelvis (as well as brain CT scan/MRI for patients with known history of brain metastatic disease) must be used at each subsequent follow-up assessment. Any other areas of disease involvement should be additionally imaged based on the signs and symptoms of individual patients.

Following the baseline assessment, efficacy for all patients will be assessed by objective tumour assessments every 8 weeks until Week 72 and every 12 weeks thereafter until objective disease progression as defined by RECIST 1.1. Any other sites at which new disease is suspected should also be appropriately imaged.

If a patient discontinues treatment (and/or receives a subsequent cancer therapy) prior to progression then the patient should still continue to be followed until objective disease progression as defined by RECIST 1.1.

Categorisation of objective tumour response assessment will be based on the RECIST 1.1 criteria of response: CR, PR, SD and PD. Target lesion (TL) progression will be calculated in comparison to when the tumour burden was at a minimum (ie, smallest sum of diameters previously recorded on study). In the absence of progression, tumour response (CR, PR, SD) will be calculated in comparison to the baseline tumour measurements obtained before starting treatment.

Following progression, patients should continue to be followed up for survival approximately every 8 weeks as outlined in the study plan.

It is important to follow the assessment schedule as closely as possible. Please refer to the study plan in [Table 3](#), [Table 4](#) and [Table 5](#).

Following the final PFS analysis data cut off for each stratum (either non HRR*m*, BRC*Am* and/or non BRC*Am* HRR*m*) objective tumour assessments should be performed as per the study schedule (see [Table 3](#), [Table 4](#) and [Table 5](#)) for patients continuing on treatment and recorded in the patient notes **but not** recorded in the eCRF.

Central reading of scans

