2. ANALYSIS SETS

2.1 Definition of analysis sets

2.1.1 Full analysis set

The full analysis set (FAS) will include all randomised patients with treatment arms assigned in accordance with the randomisation, regardless of the treatment actually received. Patients who were randomised but did not subsequently receive treatment are included in the FAS.

Patients randomized to the AZD1775+olaparib arm will be analysed as such, regardless of whether they discontinued study treatment entirely or received olaparib monotherapy after closure of the AZD1775+olaparib treatment arm in April 2019. The analysis of data using the FAS therefore follows the principles of intent to treat (ITT). All efficacy and CCI data will be summarised and analysed using the FAS. Disposition, demographic data, baseline characteristics, etc will be summarized using the FAS.

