3.3 Primary outcome measure (derivation of efficacy variables)

3.3.1 Progression-free survival

PFS is defined as the time from randomisation until the date of objective disease progression or death (by any cause in the absence of progression) regardless of whether the patient withdraws from randomised therapy or receives another anti-cancer therapy prior to progression. PFS for patients who have not progressed or died at the time of analysis will be censored at the latest date of assessment from their last evaluable RECIST assessment.

PFS will be computed as date of PFS event or censoring – date of randomisation + 1).

If, however, a patient progresses or dies after two or more missed scheduled RECIST assessments, the patient's PFS will be censored at the time of the latest evaluable RECIST assessment prior to the two missed visits.

The allowed gap between the last previous evaluable RECIST assessment and the tumour progression or death, for which the tumour progression/death will still be counted as an event, will be defined as 2 x (scheduled time between scans + allowed visit window). In details:

- If the two missed visits will occur immediately after the baseline scan then the definition of two missed visits will be calculated as 2 x (the protocol-scheduled time between scans) + the protocol-allowed visit window (since there is no need to account for an early initial visit in this case) which will be 2 x 8 weeks + 7 days + patient-specific number of days from date of randomization to date of first study treatment dose = 119 days + (patient-specific date of first study treatment dose minus date of randomization).
- If the two missed visits will occur after a post-baseline scan then the definition of two missed visits will be 2 x (the protocol-scheduled time between scans + the protocol-allowed visit window) since the previous scan may be 1 week earlier than planned and the progression visit may be 1 week later than planned.
- While a patient is in the every-8-weeks-schedule, the definition of two missed visits will be 2 x (8 weeks + 7 days) = 126 days.
- When a patient is changing from the every-8-weeks-schedule to the every-12-weeks-schedule, the definition of two missed visits will be 8 weeks + 12 weeks + 14 days = 154 days.
- While a patient is in the every-12-weeks-schedule, the definition of two missed visits will be 2 x (12 weeks + 7 days) = 182 days.

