If a patient has no evaluable visits or does not have baseline data they will be censored at Study Day 1 unless the patient dies within 17 weeks (16 weeks for two potential scans plus 1 week allowing for a late assessment within the visit window) + (patient-specific date of first study treatment dose minus date of randomization).

The PFS time will always be derived based on scan/assessment or death dates, not on visit dates. RECIST assessments/scans contributing towards a particular visit may be performed on different dates. The following rules will be applied:

- For BICR assessments, the date of progression will be determined based on the **earliest** of the scan dates of the component that triggered the progression for the adjudicated reviewer

selecting PD or of the reviewer who read baseline first if there is no adjudication for ICR data.

- For site investigator assessments, the date of progression will be determined based on the **earliest** of the dates of the component that triggered the progression.
- For both ICR and site investigator assessments, when censoring a patient for PFS the patient will be censored at the **latest** of the dates contributing to a particular overall visit assessment.

For TLs only the latest scan date is recorded out of all scans performed at that assessment for the TLs and similarly for NTLs only the latest scan date is recorded out of all scans performed at that assessment for the NTLs.

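### For primary PFS, the first missed-visit window and the 17-week death rule add a first-dose gap that the scan schedule does not support, leave the start point unsettled, and cannot be calculated for some never-dosed patients

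*SAP*

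**What the plan says.** **The window rule (SAP 3.3.1).** A progression or death after two or more missed scans is censored. The lead sentence measures the allowed gap from the last evaluable RECIST assessment to the progression or death. When the two missed scans follow directly on baseline, the limit includes the "patient-specific number of days from date of randomization to date of first study treatment dose" and comes to "119 days + (patient-specific date of first study treatment dose minus date of randomization"). Later limits are 126, 154 and 182 days and contain no dosing term.

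**The early-death rule (SAP 3.3.1).** For patients with no evaluable visits or no baseline data, "they will be censored at Study Day 1 unless the patient dies within 17 weeks". The same term, "patient-specific date of first study treatment dose minus date of randomization", is then added to the 17 weeks. The rule does not say from which date they run.

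**The scan schedule.** Protocol 5.1.1 times scans "relative to the date of randomisation and irrespective of treatment decisions, up to objective disease progression by RECIST 1.1". Protocol 5.1.2 gives "objective tumour assessments every 8 weeks until Week 72 and every 12 weeks thereafter", and the visit window is 1 week. Footnote e of Protocol Tables 4 and 5 and Appendix F Section 4.1 also count from randomisation.

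**The analysis set (SAP 2.1.1).** "Patients who were randomised but did not subsequently receive treatment are included in the FAS". All efficacy data are analysed on this set.

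**The protocol's own rule (Protocol 8.4.1).** A patient without evaluable visits or baseline data has an event if death falls within two visits of baseline. There is no dosing term. SAP Section 6 declares no change from the protocol.

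**The concern.** These two rules decide, for the primary endpoint, whether a progression or death counts or the patient is censored at the last scan or at Day 1. They also feed the event counts that trigger the 44-event interim and 68-event final analyses. A limit meant to represent two scheduled scans plus a late-visit allowance should match the schedule. Here it contains a quantity, the delay to first dose, on which the schedule does not depend. It starts from a date that varies with when the baseline scan was taken. It also needs a first-dose date that some patients in the analysis set never have. In those cases the outcome would depend on how the program treats a missing value.

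**Working it through.** **Inputs.** Scan interval 8 weeks = 56 days and visit window 7 days (Protocol 5.1.1). Dosing ideally within 3 days of randomisation, with no stated maximum (Protocol 3.5). Baseline scan before randomisation and no more than 28 days before treatment start (Protocol Table 3, footnote f). Planned olaparib PFS medians of 5 and 6 months and 68 events (SAP 1.3).

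Let g = days from randomisation to first dose, and s = days from baseline scan to randomisation. If the baseline-scan rule is kept, s + g ≤ 28.

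**1. The SAP's figures reproduce.** 2 × 56 + 7 = 119 days; 17 × 7 = 119 days. The later windows also reproduce: 2 × (56 + 7) = 126; 56 + 84 + 14 = 154; 2 × (84 + 7) = 182.

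**2. What the schedule implies.** Week 16 is day 112 after randomisation, with a window of days 105 to 119. The late edge of the second scheduled scan is therefore day 119 for every patient, whatever g is.

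**3. If the SAP window is counted from randomisation,** the limit is 119 + g:

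| g (days) | limit (day) |
|---|---|
| 0 | 119 |
| 3 | 122 |
| 7 | 126 |
| 8 | 127 |
| 14 | 133 |
| 28 | 147 |

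From g = 8 the first window exceeds the 126-day later window, although the SAP argues that the first interval needs less allowance. Even at g = 28 it closes before the Week 24 scan window opens (168 − 7 = day 161), so no third scheduled scan is absorbed.

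**4. If it is counted from the baseline scan, as the lead sentence says,** the limit falls on day 119 + g − s after randomisation:

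| s | g | limit (day) |
|---|---|---|
| 0 | 28 | 147 |
| 20 | 3 | 102 |
| 28 | 0 | 91 |

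The limit is later than day 119 only if g > s. It is earlier than the nominal Week 16 scan (day 112) once s − g > 7. Example with s = 20, g = 3: a patient misses only Week 8 and progresses on the Week 16 scan at day 112. The gap is 20 + 112 = 132 days and the limit is 119 + 3 = 122, so the event is censored after one missed scan.

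**5. Never-dosed patients.** Here g does not exist, and no fallback is given. A never-dosed patient with an evaluable post-baseline scan before the event moves to the 126-day (or later) window, which needs no dose date. Without such a scan, both limits are missing.

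**6. Size.** One undetermined event is 1/68 = 1.5% of the final count, or 1/44 = 2.3% at the interim. If there were three such patients (an assumption), 3/68 = 4.4%. For the extra days in step 3, with exponential PFS and λ = ln 2/(median × 30.4375), the chance of an event in that stretch is exp(−119λ) − exp(−(119 + g)λ). For medians of 6 and 5 months this is 0.7–0.8% at g = 3, 1.7–1.8% at g = 7 and 6.4–7.0% at g = 28. Each figure must be multiplied by the share of patients with no evaluable post-baseline scan by then, which the documents do not give.

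**The case against.** The SAP does take a dose-based view elsewhere. Table 4 in Section 4.1.4 counts scan windows from Dose Day 1, and Week 8 non-progression in Section 3.4.6 is timed from dosing. That may explain where the term came from, but it does not justify it. Table 4 serves by-visit summaries, and the interim response-rate rule in SAP 3.4.1 uses randomisation plus 49 days, which is Week 8 less the 7-day window. Neither overrides the protocol schedule or supplies a dose date for an untreated patient.

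The attrition-bias analysis (SAP 4.2.5) uses actual event times after two or more non-evaluable assessments, so part of any effect would show there. It also censors at subsequent therapy, so it is not a clean check, and it does not define the primary rule.

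The protocol's rule of two visits from baseline could serve as a fallback for never-dosed patients. That is a fair point: censoring them at Day 1 is possible, not certain.

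A reader might infer three stronger claims that the documents do not support:

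- **That late starters always get too long a window.** Counted from the baseline scan, the limit is often too short instead.
- **That every never-dosed patient who dies early has no derivable status.** Scans continue irrespective of treatment decisions, and one evaluable post-baseline scan resolves it.
- **That the arms are affected differently.** Every arm receives olaparib, and nothing in either document indicates that failure to start treatment differs by arm.

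**Conclusion.** The point holds as a specification error in an event-or-censoring rule of the primary endpoint. The dose-gap term conflicts with the randomisation-based schedule. The start point is the baseline scan in one rule and unstated in the other. The limits are undefined for never-dosed patients with no evaluable post-baseline scan before progression or death.

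The likely size is modest. The dose gap is 3 days or less if the dosing recommendation is followed. Only patients whose progression or death follows directly on baseline, without an evaluable scan in between, are touched. The range of days 91 to 147 assumes that the 28-day baseline-scan rule is kept. The number of never-dosed patients is not given, so the 4.4% figure is only an illustration. No material shift in the hazard ratio is claimed. The correction is still worth making, because it removes an avoidable judgement from the primary analysis at almost no cost.

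**What to change.** In SAP 3.3.1, before unblinding:

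1. In the first-interval rule, delete the dose-gap term and state that the limit is 119 days counted from the date of randomisation for every patient in the full analysis set, dosed or not.
2. In the early-death rule, delete the same term and state that the limit is 17 weeks (119 days) counted from the date of randomisation, again for every such patient.
3. Amend the lead sentence so that the first-interval window starts at randomisation, not at the baseline scan date. Deleting the dose term alone would shorten a window counted from the baseline scan still further. Later windows keep running from the last evaluable post-baseline scan.

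It would be tidy to align the scan windows in SAP Table 4 with randomisation at the same time. The cost is three short wording edits and the matching change in the PFS derivation program, with no new data and no effect on patients.

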3.4 Secondary outcome measures (derivation of efficacy variables)

3.4.1 Objective response rate

For the interim analyses, only patients fulfilling at least one of the following conditions will be included in the denominator of the ORR estimation:

- there is a post-baseline scan at least 49 days after date of randomization and up to the interim analysis data cut-off date, i.e., randomization date + 49 days \leq post-baseline scan date \leq interim analysis data cut-off date
- patient died up to the interim analysis cut-off date, i.e., death date \leq interim analysis data cut-off date.

For the final analyses there will be no such sub-setting in the denominator of the ORR estimation.

The assessment of ORR will only include tumour assessment data obtained up to

- progression
- last evaluable assessment in the absence of progression
- start of a subsequent anti-cancer therapy (note that for this analysis radiotherapy is not considered a subsequent anti-cancer therapy)

whatever occurs first.

ORR based on BICR is defined as the percentage of patients with at least one BICR-assessed visit response of CR or PR, with the denominator defined as the number of patients in the FAS (exception for interim analysis see above). If a total of at least 10 randomized patients had no measurable disease at baseline as per BICR, then an additional analysis of ORR will be conducted with the denominator defined as the subset of FAS patients with measurable disease at baseline as per BICR.

For sensitivity analysis, ORR is also defined as the percentage of patients with at least one visit response of CR or PR based on site investigator data, with the denominator defined as the number of patients in the FAS.

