
olaparib maintenance therapy compared with patients with no evidence of *BRCA* or other HRR gene mutations. Separation of the KM curves for PFS in favour of olaparib was observed for the 21 patients with tumours that were non *BRCA* HRRm, but not in the 58 patients with tumours where no HRR mutation was detected (Hodgson et al 2015).

Olaparib monotherapy was investigated in a Phase 2 multicentre study in women with high-grade serous ovarian carcinoma (HGSOC) or TNBC receiving olaparib 400 mg bd capsules (Gelmon et al 2011). Patients were stratified according to *BRCA1* or *BRCA2* mutation or no known mutation. Ninety patients of the 91 enrolled received treatment (HGSOC n=64 and TNBC n=26). Of the HGSOC patients with *BRCA1* or *BRCA2* mutations, objective response was observed in 7/17 patients (41%; 95% CI 22%-64%). Response was observed in 11/46 patients (24%; 95% CI 14%-38%) without known mutations.

Olaparib monotherapy has been investigated in Phase 2 and Phase 3 studies in metastatic or advanced breast cancer. In the Phase 2 study, women with confirmed *BRCA1* and *BRCA2* mutation, with advanced breast cancer and a median of 3 prior chemotherapy regimens before entering the study were administered olaparib in two sequential dosing cohorts. Cohort 1 (n=27) were administered olaparib 400 mg capsules bd, and cohort 2 (n=27) were given an olaparib 100 mg capsule bd. In cohort 1 (400 mg bd), objective response was observed in 11 (41%) of 27 patients (95%; CI 25%-59%), and 6 (22%) of 27 patients (95%; CI 11%-41%) in cohort 2 (100 mg bd) (Tutt et al 2010). In the Phase 3 study, women with TNBC or ER/PR⁺ breast cancer (who were not eligible for further endocrine therapy) and confirmed *BRCA1* and *BRCA2* mutations were randomised to receive olaparib monotherapy (300 mg tablet bd) (n=205) or Physician's choice of chemotherapy (capecitabine, vinorelbine, or eribulin) (n=97). Median PFS of patients who were ER or PgR negative, as assessed by blinded central review, was 5.6 months for the olaparib arm compared with 2.7 months for the chemotherapy arm (HR=0.39, p<0.009). The ORR, as assessed by blinded central review, for all patients, was 59.9% for the olaparib arm (95%; CI 52.3%-67.4%), and 28.8% in the chemotherapy arm (95%, CI 18.3%-41.3%) (Krammer et al 2017).

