CRF. AstraZeneca retains the right to request additional information for any patient with ongoing AE(s)/SAE(s) at the end of the study, if judged necessary. Patients should be seen at least 30 days after discontinuing study medication to collect and/or complete AE information. For guidance on reporting AEs after the 30-day follow up period see Section 6.3.1.1.

Any patient who has not yet shown objective radiological disease progression at withdrawal from IP should continue to be followed as per RECIST 1.1.

All patients must be followed for survival, up to the final OS analysis (i.e. when OS data for the ceralasertib+olaparib vs. olaparib monotherapy pairwise comparison is approximately 70% mature).

If a patient is withdrawn from study, see Section 3.9.

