3.2.1 RECIST-based assessments by Blinded Independent Central Review

BICR of all radiological imaging data will be carried out using RECIST version 1.1. All radiological scans for all patients (including those at unscheduled visits, or outside visit windows as defined in Section 4.1.4) will be collected on an ongoing basis and sent to PAREXEL for BICR. The independent reviewers will be blinded to study treatment.

For each post-baseline visit scan, the BICR will define the RECIST 1.1 overall visit response of CR, PR, SD or PD depending on the status of their disease compared with baseline and previous scans by assessing target lesions (TLs), non-target lesions (NTLs) and new lesions. If a patient has had a tumour assessment that cannot be evaluated, then the patient will be assigned a visit response of NE unless there is evidence of progression in which case the response will be assigned as PD. No programmatic derivation of visit response is necessary.

The date of progression will be provided (by each reviewer) based on the earliest of the scan dates of the component that triggered the progression.

If adjudication is performed, the reviewer that the adjudicator agreed with will be selected as a single reviewer (note in the case of more than one review period, the latest adjudicator decision will be used). In the absence of adjudication, the records for all visits for a single reviewer will be used. The reviewer selected in the absence of adjudication will be the reviewer who read the baseline scan first. The records from the single selected reviewer will be used to report all BICR RECIST information including dates of progression, visit response, censoring and changes in target lesion dimensions. Endpoints will be derived programmatically from this information.

Results of this independent review will not be communicated to investigators and the management of patients will be based solely upon the results of the RECIST 1.1 assessment conducted by the investigator.

Further details of the BICR are documented in the Independent Review Charter.

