4.2.8.3 Analysis of objective response based on BICR for all five patient populations

Note: take into account the statement in Section 3.4.1 on the denominator when calculating percentages for ORR.

Frequency tables by treatment arm will be produced that present

- number and percentage of patients with / without objective response (the former is the ORR) according to BICR
- number and percentage of patients with / without objective response according to site investigator assessment.

Objective response will be analysed using logistic regression with covariates study treatment and prior platinum-based therapy (no/yes). The results of the analysis will be presented in terms of odds ratio comparing treatment arms in pairwise manner together with associated 90% profile likelihood CI (using the option 'LRCI' in SAS PROC GENMOD) and 2-sided p-value. P-values will be based on twice the change in log-likelihood resulting from the addition of covariate study treatment to the model containing only the covariate related to prior platinum-based therapy. The three pairwise odds ratio will be the following:

- objective response odds ratio for AZD6738+Olaparib over Olaparib alone
- objective response odds ratio for AZD1775+Olaparib over Olaparib alone
- objective response odds ratio for AZD6738+Olaparib over AZD1775+Olaparib.

If there are not enough responses for a meaningful analysis using logistic regression then a Fisher's exact test using mid p-values will be presented for each pairwise comparison of treatment arms. The mid-p-value modification of Fisher's exact test amounts to subtracting half of the probability of the observed table from Fisher's p-value, i.e., mid p-value = 2-sided p-value – table probability/2.

A sensitivity analysis of objective response using site investigator data will be performed.

4.2.8.4 Analysis of duration of response based in BICR for the 3 primary patient populations

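### The interim ORR denominator depends on having been scanned or having died, so any living early progressors and unscanned leavers drop out and interim ORR is then overstated

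*SAP*

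**What the plan says.** SAP 3.4.1 sets a special denominator for ORR at the interim analyses. A patient counts if at least one of two conditions holds: "there is a post-baseline scan at least 49 days after date of randomization and up to the interim analysis data cut-off date", or "patient died up to the interim analysis cut-off date". At the end the restriction is lifted: "For the final analyses there will be no such sub-setting in the denominator of the ORR estimation". BICR-based ORR is otherwise a percentage of the FAS, with the interim exception noted in the definition itself. SAP 2.1.1 keeps every randomised patient in the FAS, treated or not.

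The paragraph on investigator-based ORR in SAP 3.4.1 names the FAS without repeating the exception. SAP 4.2.8.3, which covers both the BICR and the investigator tables, tells the analyst to "take into account the statement in Section 3.4.1 on the denominator when calculating percentages for ORR".

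Three other provisions decide who meets the first condition.

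- Protocol 5.1.1 schedules scans every 8 weeks with a one-week window, "up to objective disease progression by RECIST 1.1".
- SAP 3.2.1 sends all scans for central reading, "including those at unscheduled visits, or outside visit windows as defined in Section 4.1.4".
- Protocol 3.8.1 keeps patients who merely stop treatment under tumour assessment: "Any patient who has not yet shown objective radiological disease progression at withdrawal from IP should continue to be followed as per RECIST 1.1".

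**The concern.** An interim response rate has good reason to leave out patients randomised too recently to have had a first scan. The rule in SAP 3.4.1 does that, but it also removes patients who had ample time and have no qualifying scan. Two groups are exposed:

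- patients with progression on an unscheduled scan before day 49, alive at the cut-off, whose scanning has normally ended;
- patients alive at the cut-off who were lost or withdrew before any scan.

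Both are non-responders in the final FAS denominator. Removing them at the interim leaves the numerator alone and shrinks the denominator. The death clause adds an asymmetry: an early progressor who has died stays in, while an otherwise identical one who is alive goes out.

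Elsewhere the plan handles such a patient as a failure. SAP 3.4.6 carries a progression seen before Week 8 forward to Week 8, and SAP 3.3.1 makes it a PFS event. One review package could therefore show a patient as a PFS event and leave the same patient out of ORR. At stake is a supportive figure read by the Unblinded Review Committee (URC) beside the interim PFS results.

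**Working it through.** **The threshold.** The plan states no ORR figure to reproduce. The 49 days do follow from its schedule: first scan at 8 × 7 = 56 days, window 7 days, earliest 56 − 7 = 49 and latest 56 + 7 = 63. Progression before day 49 can therefore normally be found only on an unscheduled scan.

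**The formula.** Let N be the patients who should count, R the responders, m the non-responders wrongly dropped, p = R/N and f = m/N. The rule gives R/(N − m) = p/(1 − f). The overstatement is p/(1 − f) − p = p×f/(1 − f), which is positive whenever f > 0.

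**Closed form at p = 30% (an assumed rate).**

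- f = 2%: 0.30 × 0.02/0.98 = 0.6 point
- f = 4%: 0.30 × 0.04/0.96 = 1.25 points
- f = 8.5%: 0.30 × 0.085/0.915 = 2.8 points
- The overstatement passes 3 points only when f exceeds 0.03/0.33 = 9.1%.

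**In patients.** The simulation below has about 43 assessable patients per arm at the interim. With 13 responders:

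- none dropped: 13/43 = 30.2%
- one dropped: 13/42 = 31.0%
- two dropped: 13/41 = 31.7%

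The standard error is √(0.3 × 0.7/43) = 0.070, so the 90% half-width is 1.645 × 0.070 = 0.115, about 12 points.

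**Simulation.** Taken from the documents: the PFS medians, 50 patients per arm, the 44-event interim and the scan schedule. Assumed: uniform accrual over 15 months, first scan on days 49 to 63, median survival after progression of 8 months, and the rates in the table. Capture is the share of progressions before day 49 that are found on an early scan; leavers are patients who go unscanned. The comparator is a denominator of all patients randomised at least 63 days before the cut-off. There were 4,000 runs per scenario, with true ORR 30% in both arms.

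| Capture / leavers | f, control; combination | Overstatement in points, control; combination | Shift in between-arm difference, points |
|---|---|---|---|
| 0% / 0% | no one wrongly dropped | −0.2; 0.0 | 0.1 |
| 25% / 2% | 4.0%; 3.2% | 1.18; 0.94 | −0.2 |
| 50% / 5% | 8.5%; 6.8% | 2.72; 2.15 | −0.6 |

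With true ORRs of 20% and 30% in the two arms and equal capture, the difference moved by 0.0, 0.1 and 0.35 point. With 50% capture in one arm, none in the other and 2% leavers, it moved by −1.7 or +1.1 points, depending on which arm had the early scans.

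**A second simulation**, on different assumptions (56-day comparator, two arms pooled, median OS 10 or 18 months, capture 0 to 50%, leavers 0 to 8%), gave −0.1 point with neither group present and +0.1 to +3.0 points otherwise. The slight negative arises because the death clause also admits recently randomised patients who died, about 0.2 to 0.3 per interim.

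**The case against.** The strongest reply is that this is a disclosed interim choice. SAP 3.4.1 marks the exception inside its own definition and restores the full FAS at the end. A reader might infer that it contradicts the FAS definition; it does not. What stands against the rule is narrower: it screens on an outcome where a date would do.

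The affected group is also limited. Patients who only stop treatment stay under assessment, early progressors who die by the cut-off come back in, and Protocol 5.1.1 allows a further assessment when central review does not confirm progression. A responder seen only before day 49 would drop out too, which works the other way but should be rare.

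A reader might infer that interim ORR is biased upward as such. The documents do not support that, because they give no frequency for either group, and with neither present the bias is zero or slightly negative.

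A reader might also apply the rate in Protocol 1.2.1: "The ORR, as assessed by blinded central review, for all patients, was 59.9% for the olaparib arm". At that rate the two non-zero scenarios give simulated overstatements of 1.80 to 5.07 points. But that trial enrolled patients with *BRCA* mutations and included hormone-receptor-positive disease. At most it bears on stratum A here, and the first PFS interim is expected in stratum C.

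Finally, a reader might infer that the April 2019 review was affected. The ORR tables proper are marked only from the second URC review. The investigator best-response table (T 11.2.2.6.1) is also marked for the first, but nothing says the denominator rule governs it, and that review preceded SAP version 2.0.

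**Conclusion.** The point holds conditionally, and it is minor. The mechanism and direction follow from the text: if any living patients progress on a scan before day 49 or leave unscanned, interim ORR is overstated by p×f/(1 − f). The size rests on an f that the documents do not give. It is about zero (−0.1 to −0.2 point) if there are no such patients, under 2 points for one or two of 43 at about 30% ORR, and about 1 to 2.7 points under the assumed 25% to 50% capture and 2% to 5% leavers. With equal capture in both arms the between-arm difference moved by less than 1 point in every simulated case. It moved more only when capture was assumed to be one-sided, which an open-label design permits but the documents do not show.

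The reach is the supportive interim ORR tables for the second and later URC reviews. Final ORR, PFS and the non-progressive-disease criterion are unaffected. These documents state no ORR threshold; details of the PFS interims are left to the URC Charter, which is not among them.

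**What to change.** In SAP 3.4.1, replace the two interim conditions with one on time: the interim ORR denominator is all FAS patients randomised at least 63 days (8 weeks plus the one-week window) before the interim cut-off. Count everyone in it without a response as a non-responder, whether or not scanned. State that the same denominator applies to BICR and investigator ORR, as SAP 4.2.8.3 already implies.

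The cost is one sentence and a date filter. The downside is that a few recent patients already scanned on days 49 to 62 are left out. In the simulation the denominator fell from 43.7 to 42.8 (control) and from 43.5 to 42.6 (combination), about one patient per arm. That figure assumes uniform accrual, whereas the plan expects non-linear recruitment, so it could differ. A patient whose first scan is delayed beyond day 63 would count as a non-responder until scanned, which is a small conservative effect.
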